#### 7.4.1 Protection of Participant Data

The Sponsor and any designated CROs will make every reasonable effort to protect the confidentiality of the participants participating in the study. Except as required by law, participants will not be identified by name, social security number, address, telephone number, or any other direct personal identifier. A unique identification code will be assigned to each participant participating in this study. Information about the code will be kept in a secure location by the Investigator. All participant data will be stored in locked offices. All electronic data will be password-protected on computers stored in locked offices. Access to participant information will be limited to study personnel only. Any data, including photographs, that may be published in abstracts, scientific journals, or presented at medical meetings will reference a unique participant code and will not reveal the participant's identity without the express approval of the participant. It is possible that participant personal health records may be disclosed to other agencies such as regulatory bodies as per country regulations.

Data storage will reside at the clinical research sites and at Rani Therapeutics. Sites will retain data collected during the clinical trial for a minimum of 15 years. Sponsor will retain data per company Standard Operating Procedures.

The HIPAA requirements affect clinical trials in three key areas as described below:

- **Accounting of Disclosures:** Data collected during the conduction of prescreening activities for this clinical trial are participant to the HIPAA accounting of disclosures' regulations. It is the responsibility of the investigative center to tell all participants whose records were screened for eligibility in the trial that their records were used in this manner if he or she requests an accounting of when his or her data were disclosed.
- **Consent:** All participants in the clinical trial will be made aware that their participation in the clinical trial will involve disclosure of certain protected health information to Rani Therapeutics and for what purpose. The Informed Consent form will contain a listing of the type of information that will be disclosed during the clinical trial.
- **Withdrawal of Consent:** HIPAA specifically allows companies such as Rani Therapeutics participant to jurisdiction of the FDA access to protected health information for activities related to the quality, safety or effectiveness of devices. This means that Rani Therapeutics can use data from this clinical trial even if the individual withdraws his or her authorization.

#### 7.5 Participant Accountability

Following completion of screening, participants will be assigned to their age group and have one study visit to swallow the Mock-RP and complete questionnaires ([Figure 2](#)).

[figure not shown]

Figure 2: Participant Accountability Overview

Screening and visit requirements are outlined in Table 1.

Table 1: Screening and Visit Requirements

	Swallow Visit
Inclusion/Exclusion criteria review	✓
Informed Consent	✓
Medical Hx/Demographics	✓
Weight/Height/Temperature	✓
Concomitant Medications	✓
Urine Pregnancy Test	✓ ^
Dispense Mock-RP	✓
Questionnaires	✓
Dispense Calcium Pill, if necessary	✓ *
Adverse Event(s)	✓

^ Pregnancy test completed on day of screening.

\* Dispense ONLY if participant is unable to swallow the Mock-RP

## 7.6 Screening Procedures

All participants currently using injections at each participating investigational site should be evaluated for study eligibility. Participants may be recruited from clinical site databases, general population, using flyers, broadcast or web-based/social media. For participants who appear to meet study criteria, the Investigator (or designee) will discuss the study with the potential participant and ask him/her to consider study participation. Along with other required elements, the background and purpose of the study, participation requirements, the potential benefits and risks of participation must be explained to the participant. If he/she agree, an Informed Consent Form (ICF) must be signed to document the consenting process. Prior to any non-standard-of-care procedures, the participant must sign the Informed Consent Form approved for use by the IRB. Participants must be provided a copy of the signed ICF for their reference.

### 7.6.1 Pill Swallowing Issues

Participants will report if they have issues swallowing pills.

### 7.6.2 Clinical Examination

A medical history focusing on, but not limited to, the 90 days before study day will be obtained. The history will review the use of medications, including prescription and non-prescription pharmaceuticals per Section 7.6.3 “Concomitant Medications, Treatments, and Procedures”.

Height, weight, and temperature will be measured before administration of the Mock-RP capsule.

### 7.6.3 Concomitant Medications, Treatments, and Procedures

The concomitant prescription and non-prescription pharmaceuticals must be reported in the CRF at screening. For this protocol, a prescription medication is defined as one that can be prescribed only by a licensed physician.

#### 7.6.4 Urine Collection for Pregnancy

In women of childbearing potential, urine pregnancy tests will be performed the day of the study. Pregnancy tests are not required for surgically sterile or postmenopausal women. Tests will be performed on-site and results must be known before administration of the study CTM.

### 7.7 Visit Procedures

#### 7.7.1 Pre-Swallow Questionnaire

Participant will complete the pre-swallow questionnaire to self-report any historical issues with swallowing pills, current medicines they take in pill form, and if they would take an alternative therapy in pill form.

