General Study Design	A prospective, single-center, open-label, single-arm, observational study enrolling up to 200 men and women volunteers age $\geq 21$ currently using injection therapy to treat chronic disorders (e.g., diabetes (I or II), rheumatoid arthritis, ulcerative colitis, Crohn's disease, ankylosing spondylolisthesis, psoriasis, growth hormone deficiency, hemophilia A) recruited from the general population with up to 150 participants attempting to swallow the Mock-RP after passing protocol required screening. A total of 30 to 50 participants will be included in each of the following age ranges: 21-50, 51-65, 66-75. Participants must meet all inclusion and none of the exclusion criteria prior to attempting to swallow the Mock-RP. Participants will complete a questionnaire on their thoughts on an alternative therapy in pill form. Upon completion of the questionnaire, participants will be requested to swallow a Mock-RP. The Mock-RP will be a standard 000 capsule filled with potato starch weighing similar to the RaniPill™ Capsule. The capsule is protected by an enteric coating with colorant and lubricious coating allowing intact passage through the stomach into the jejunum, where the pH starts dissolving the coating; completely dissolving in the small intestine. After swallowing the Mock-RP, the participant will complete the questionnaire assessing swallowability of the Mock-RP. If the participant was unable to swallow the Mock-RP, they will be asked to attempt to swallow a Calcium dietary supplement (Rapid Release Calcium in Liquid Softgel). Anticipated participant duration is approximately 1 hour.
Inclusion Criteria	Individuals eligible to participate in this study must meet all the following criteria: 

1. Participant age is 21 – 75 years

2. Participant understands the nature of the study, is willing to comply with protocol defined evaluations, and provide written informed consent

3. Participant currently taking injections to treat a chronic disorder

4. Non-pregnant, non-lactating female

 NOTE: Females who are of childbearing potential must have had a negative pregnancy test on day of screening

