## 4 METHODOLOGY AND ENDPOINTS

The objective of this study is to assess a participant's ability to swallow a Mock-RP.

Eligible participants will complete a questionnaire to assess their experience on an alternative therapy in pill form. Upon completion of the questionnaire, participants will be requested to swallow a Mock-RP then complete a questionnaire assessing a participant's ability to swallow the Mock-RP. Anticipated participant duration is approximately 1 hour.

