### 4.1 Study Endpoints

Several endpoints will be evaluated, including:

- Percent of participants successfully swallowing the Mock-RP as reported on the questionnaire.
- Assess if participant would choose a pill instead of their current injection therapy if a pill becomes available.
- Participant experience with swallowing Mock-RP stratified by number of years using injections.
- Participant experience with swallowing Mock-RP stratified by age (21-50, 51-65, 66-75 years).
- Participant experience with swallowing Mock-RP stratified by frequency of injection treatment.
- All adverse events categorized by type and frequency.

	PILL SWALLOW STUDY PROTOCOL	Doc No.:	CP-0003
		Revision:	C
		Page:	Page 11 of 12

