#### 7.7.3 Post-Swallow Questionnaire

Participant should complete the post-swallow questionnaire to report the palatability and swallowability of the Mock-RP.

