## 13 STATISTICAL METHODS

Categorical data will be summarized using frequency tables, presenting the participant counts and relative percentages. Continuous variables will be summarized by the mean, standard deviation, median, minimum and maximum. The SAS system or equivalent statistical package will be used to perform all analyses. Exact confidence intervals will be generated for estimates of proportions. Asymptotic confidence intervals will be generated for estimates of means. Except where otherwise noted, p-values of all tests will be reported without any correction for the multiplicity of tests performed.

	PILL SWALLOW STUDY PROTOCOL	Doc No.:	CP-0003
		Revision:	C
		Page:	Page 26 of 27

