### **13.2 Sample Size Justification**

As an observational study, no hypothesis tests are planned. All data will be summarized. Nevertheless, with the sample size proposed for the study, the following levels of precision of the estimates, expressed as the width of the confidence interval, can be achieved:

1. The width of the exact 95% two-sided confidence interval for percentages will be no wider than +/- 14.5% with 50 participants contributing to the estimate of the proportion and will be no wider than +/- 8.3% with 150 participants.
2. The width of the 95% two-sided confidence interval for the mean will be equal to +/- 27.7% of the standard deviation with 50 participants contributing to the estimate of the mean and will be equal to +/- 16.0% of the standard deviation with 200 participants.

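### As described, the preference item asks whether participants would accept a pill, while the endpoint is whether they would choose it over their injection; scoring a yes as the endpoint could overstate choice

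*Combined protocol and SAP*

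**What the plan says.** The endpoint is worded identically in the Synopsis and in 4.1: "Assess if participant would choose a pill instead of their current injection therapy if a pill becomes available". It is a choice between two named options.

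The pre-swallow questionnaire is described in three places. Section 7.7.1 lists its topics as past problems with swallowing pills, medicines now taken as pills, "and if they would take an alternative therapy in pill form". The Synopsis says: "Participants will complete a questionnaire on their thoughts on an alternative therapy in pill form". Section 4 says: "Eligible participants will complete a questionnaire to assess their experience on an alternative therapy in pill form". None of the three names the injection or gives response options.

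The post-swallow questionnaire (7.7.3) is there "to report the palatability and swallowability of the Mock-RP"; no choice item is described for it.

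On analysis, section 13 says "Exact confidence intervals will be generated for estimates of proportions", and 13.2 adds "As an observational study, no hypothesis tests are planned". Neither says which answer counts as choosing the pill, or how indifferent or undecided answers are handled.

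**The concern.** Willingness and choice are different quantities. Someone can be ready to take a pill and still have no preference, or prefer to stay on the injection. Such a person answers yes to the item as described but does not meet the endpoint as defined.

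If the first quantity is reported under the name of the second, the study gives an acceptability rate in place of a choice rate. Section 2.3 makes patients' selection of oral therapy over their present injections part of the reason for the study, so this figure is likely to be read and used. The error would not shrink with more participants and would not show in the confidence interval. With one visit and no planned follow-up, a comparison that was not asked for cannot readily be recovered later.

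**Working it through.** **1. The plan's own precision figures.** Section 13.2 states that the exact 95% interval will be "no wider than +/- 14.5% with 50 participants contributing to the estimate of the proportion", and no wider than +/- 8.3% with 150. The exact (Clopper-Pearson) limits for x out of n are the 2.5% quantile of Beta(x, n-x+1) and the 97.5% quantile of Beta(x+1, n-x). Taking the largest half-width over all x:

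- n = 50: largest at x = 25, limits 35.5% to 64.5%, half-width 14.47%.
- n = 150: largest at x = 75, limits 41.7% to 58.3%, half-width 8.26%.

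Both round to the stated figures. They are the same whichever way the item is worded, so the question is one of bias and not of precision.

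**2. Direction and size of the bias.** Anyone who would choose the pill would also take it, so choosers are a subset of those willing:

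- percent willing = percent choosing the pill + percent willing but not choosing it.
- bias, if willing is scored as choosing = percent willing but not choosing it, which is zero or positive.

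The sample size does not enter.

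**3. Illustration.** The documents give no figure for the last term. The inputs here are assumptions: 60% true choosers, and a willing-but-not-choosing share between 0 and 30 points. With n = 150:

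| Assumed share | Count scored yes | Reported | Exact 95% interval |
|---|---|---|---|
| 0 points | 90/150 | 60% | 51.7% to 67.9% |
| 10 points | 105/150 | 70% | 62.0% to 77.2% |
| 20 points | 120/150 | 80% | 72.7% to 86.1% |
| 30 points | 135/150 | 90% | 84.0% to 94.3% |

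From 10 points upward, the interval no longer contains the assumed true 60%.

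In one age group of 50, a 10-point share gives 35/50 = 70%, interval 55.4% to 82.1%, which still contains 60%. A 20-point share gives 40/50 = 80%, interval 66.3% to 90.0%, which does not.

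**4. Thresholds against the plan.** A share above about 8 points exceeds the stated maximum half-width at n = 150, and a share above about 14 points exceeds it at n = 50. The maximum half-width is reached at 50%. At a reported 70% with n = 150 the half-width is (77.2 - 62.0)/2 = 7.6 points, so using the maximum does not exaggerate the comparison.

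**The case against.** The strongest reply is that 7.7.1 is a one-sentence list of topics, not the form. The protocol's summaries are known to be incomplete: 7.7.3 mentions only palatability and swallowability, yet 7.7.4 cites a specific yes/no item from that form, and the change order shows that it also carries a visual analogue scale. The comparator may also be implied. Every eligible participant is on injections, so an alternative in pill form can naturally be read as an alternative to the injection.

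Both points stand. A reader might infer that the form asks only about willingness, or that indifferent people are in fact counted as choosing the pill. The documents support neither: the form is not shown, and no scoring rule exists. The conclusion has to stay conditional.

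Three further readings should not be pressed:

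- Calling the questionnaire an assessment of experience in section 4 is loose editing. The parallel Synopsis sentence speaks of thoughts, and there is no evidence of a separate measurement.
- A reader might want the item to fix how often the pill is taken, or to assume equal benefit. The endpoint's only premise is that a pill becomes available, so adding these would change the endpoint.
- Any particular size for the overstatement only restates an assumed share.

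It is also fair to say that the study's objective is ability to swallow, that preference is one of several unranked descriptive endpoints, and that no sample size or stated figure changes. This limits the weight of the point. It does not remove it, because no described item or analysis rule supplies the comparison that the endpoint needs.

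**Conclusion.** The point holds in conditional form. The described item does not clearly measure the stated endpoint. If it is used as described and a yes is scored as choosing the pill, the reported percentage is too high by exactly the share who would take a pill but would not choose it over their injection.

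That share is unknown. It could be zero, in which case nothing is lost; an assumed 10 points would exceed the plan's stated maximum half-width of 8.3 points at n = 150. The documents do not show that the overstatement will occur, only that the plan as written does not prevent it and could not reveal it. If the actual form already asks the comparative question, aligning the protocol text and stating the scoring is enough. This is a cheap improvement to a stated endpoint, not a threat to the study's main objective.

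**What to change.** Word the item so that it matches the endpoint, and give it verbatim in 7.7.1. For example: *If a pill became available, would you choose: the pill / my current injection / no preference.* In section 13, define the endpoint as the percentage choosing the pill, with an exact 95% interval and a stated denominator, and report the no-preference percentage separately. Use the same description of the item in the Synopsis, section 4 and 7.7.1.

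The cost is at most one reworded questionnaire item and an IRB submission of the revised form. Sample size and visit procedures do not change. The downside for the sponsor is that the reported percentage may be lower.

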#### 7.7.2 Mock-RP Swallowing

The participant should rinse their mouth with water before swallowing the Mock-RP then swallow the pill the way they always swallow pills, without chewing. While swallowing, the participant should take into account how the pill feels on the surface of their tongue and palate.

#### 7.7.3 Post-Swallow Questionnaire

Participant should complete the post-swallow questionnaire to report the palatability and swallowability of the Mock-RP.

#### 7.7.4 Calcium Pill Swallowing, if necessary

Participants unable to swallow the Mock-RP on the post-swallow questionnaire (responded “No” to “Did you manage to swallow the pill?”) will be asked to attempt to swallow a Calcium dietary supplement (Rapid Release Calcium in Liquid Softgel – contains 600 mg calcium as calcium carbonate per softgel and 500IU Vitamin D as D3 Cholecalciferol per softgel). The participant should rinse their mouth with water before attempting to swallow the calcium pill then swallow the pill the way they always swallow pills, without chewing.

#### 7.7.5 Unscheduled Visits

Participant study duration will be approximately 1-hour; thus, no unscheduled visits are anticipated in this study.

#### 7.7.6 Participant Withdrawal Criteria

Participants can withdraw from the study at any time for any reason; the reason for withdrawal will be documented. All data available at the time of withdrawal (if any) will be used for analysis. There will be no further data collection per this study Investigation Plan on the participant who has withdrawn.

## 8 INVESTIGATIONAL CTM HANDLING AND TRACEABILITY

The Mock-RP is investigational and will be tracked from the time it is shipped and/or hand carried from Rani Therapeutics until it is either used in the study or returned to the sponsor. A CTM

Accountability Log will be maintained at each study site and will be provided by Rani Therapeutics in the Regulatory Binder. CTM allocated for site use will be recorded in the CTM Accountability Log upon delivery to the study site and will be stored in a secured area until use. The log should include:

- name(s) of person(s) who received used, returned, or disposed of the CTM
- The date of receipt, identification, and quantity of each CTM
- The expiry date, if applicable
- The date of use
- Participant identification
- The date of return of unused or expired CTM, if applicable
- The date and documentation of disposal of the CTM as per instructions of the sponsor, if applicable.

All unused study CTM must be returned to Rani Therapeutics.

## 9 STUDY DEVIATIONS

A study deviation is defined as an event within a study that did not occur according to the protocol or the CTA. Prior approval by Rani Therapeutics and IRB is expected in situations where the investigator anticipates, contemplates, or wishes to make a conscious decision to deviate if the deviation affects participant's rights, safety, and well-being, or the scientific integrity of the clinical investigation. Prior approval is not required when a deviation is necessary to protect the life or physical well-being of a participant in an emergency or in unforeseen situations beyond the investigator's control (e.g., participant failure to attend scheduled follow-up visits, inadvertent loss of data due to a computer malfunction, etc.). All study deviations must be reported regardless of whether medically justifiable, pre-approved by Rani Therapeutics, an inadvertent occurrence, or done to protect the participant in an emergency. The deviation must be recorded and documented in participant medical/research record with an explanation for the deviation. Reporting of deviations must comply with IRB policies, local laws, and/or regulatory agency requirements, if applicable.

The PI shall notify Rani Therapeutics and the reviewing IRB of any deviation from this CIP affecting the participant's rights, safety, and well-being of human participants under emergency circumstances. Notification must be given as soon as possible, but in no later than 5 working days after the emergency occurred. Rani Therapeutics is responsible for analyzing deviations, assessing their significance, and identifying any additional corrective and/or preventive actions (e.g., amend the CIP, conduct additional training, etc.). Repetitive or serious investigator compliance issues may require initiation of a corrective action plan with the investigator, and in some cases, necessitate suspending site enrollment until the problem is resolved or ultimately terminating the investigator's participation in the study.

## 10 ADVERSE EVENTS DEFINITIONS AND REPORTING

### 10.1 Adverse Event

Adverse Event (AE): Any untoward medical occurrence, unintended disease or injury, or untoward clinical signs (including abnormal laboratory findings) in participants, users or other persons whether or not related to the investigational CTM.

### 10.2 Serious Adverse Events (SAE)

An adverse event is considered serious when it:

- Led to death,
- Led to serious deterioration in the health of the participant, that either resulted in
  - A life-threatening illness or injury, or
  - Permanent impairment of a body structure or a body function, or
  - In-patient or prolonged hospitalization, or
  - Medical or surgical intervention to prevent life-threatening illness or injury or permanent impairment to a body structure or a body function,
- Led to fetal distress, fetal death or a congenital abnormality or birth defect

All SAEs will be reported on the SAE report form.

